#### 10.6 Progression-Free Survival

From date of registration to date of first documentation of progression or symptomatic deterioration (as defined above), or death due to any cause. Patients last known to be alive without report of progression are censored at date of last contact.

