#### FOOTNOTES

- \* Physical exam and medical history must be completed within 28 days prior to registration (see [Section 5.3a](#)).
- △ Continuous oral daily dosing (see [Section 7.1](#)).
- Ω Protocol treatment and parameters will continue at these intervals until off protocol treatment per [Section 7.6](#). While on protocol treatment, disease assessments will continue every 8 weeks until progression. If patient is removed from protocol treatment prior to disease progression, assessments will be continued on this schedule until disease progression.
- √ After disease progression, follow-up will occur (with lab tests and scans performed at the discretion of the treating investigator) every 3 months for the first year and then every 6 months thereafter for up to three years after registration or until death.
- ≠ Tumor assessment will be done after every second cycle by the same method used at baseline. REMEMBER, RESPONSE SHOULD BE CONFIRMED BY A SECOND DETERMINATION AT LEAST 4 WEEKS AFTER A COMPLETE OR PARTIAL RESPONSE HAS BEEN NOTED.

CLOSED EFFECTIVE 05/10/16

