### 11.2 Analysis of Primary Endpoint

#### Arm 1: ARQ 197 as a single agent (35 patients):

With no activity of ARQ 197 as a single agent in pRCC, we would expect a response rate of 10%. We would consider ARQ 197 promising for further investigation if the response rate were  $\geq 30\%$ . Initially, 20 eligible patients will be accrued to this arm of the study. If 0-1 patients are responders, this would constitute lack of evidence of sufficient activity, and this arm would be closed to accrual. We would expect this to occur 1% of the time if the true probability of response was 30%. If this arm shows adequate activity in the first stage, and toxicity and safety considerations permit, accrual will continue until a total of 35 eligible patients are accrued. If the total number of patients out of 35 who respond is 8+, we would consider this agent promising and worthy of further investigation in pRCC if toxicity and PFS data are also supportive. In this arm, the design has a significance level (probability of falsely declaring that an agent with a 10% response probability is worthy of further investigation) of 2%, and a power (probability of correctly declaring that an agent with a response rate of 30% is worthy of further investigation) of 87%. Thirty five eligible patients are sufficient to estimate the confirmed response to within  $\pm 17\%$  (95% confidence interval).

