#### 14.4 Data Submission Overview and Timepoints

- a. WITHIN 7 DAYS OF REGISTRATION:

Submit the following:

**S1107** Advanced Renal Carcinoma Onstudy Form

Baseline Tumor Assessment Form

**S1107** Baseline Abnormalities Form

Radiology reports from all scans performed to assess disease at baseline

Pathology Report

- b. WITHIN 28 DAYS OF REGISTRATION:

Submit materials outlined in [Section 15.0](#) to Lab #201.

- c. WITHIN 7 DAYS OF COMPLETION OF EACH CYCLE WHILE ON PROTOCOL TREATMENT:

Submit the **S1107** Treatment Form and **S1107** Adverse Event Form documenting required parameters as specified on the Study Calendar.

- d. WITHIN 14 DAYS AFTER EVERY DISEASE ASSESSMENT, AFTER EVERY SECOND CYCLE WHILE ON PROTOCOL TREATMENT; IF PATIENT HAS NOT PROGRESSED ONCE OFF PROTOCOL TREATMENT THEN CONTINUE TO SUBMIT EVERY 8 WEEKS UNTIL PROGRESSION:

Submit the Follow-Up Tumor Assessment Form and all Radiology Reports until documented disease progression per [Section 10.2d](#) or removal from protocol treatment.

- e. WITHIN 14 DAYS OF DISCONTINUATION OF TREATMENT:  
Submit the Off Treatment Notice and final **S1107** Treatment Form and **S1107** Adverse Event Form.
- f. AFTER OFF TREATMENT, EVERY 3 MONTHS FOR THE FIRST YEAR AND THEN EVERY 6 MONTHS UNTIL DEATH OR FOR A MAXIMUM OF 3 YEARS:  
Submit the Follow-Up Form.
- g. WITHIN 14 DAYS OF PROGRESSION/RELAPSE:  
Submit a Follow Up Tumor Assessment Form, Radiology Report, **S1107** Treatment Form and **S1107** Adverse Event Form (if the patient was still on protocol treatment) or Follow-Up Form (if the patient was off protocol treatment) documenting date, site and method for determining progression/relapse.
- h. WITHIN 4 WEEKS OF KNOWLEDGE OF DEATH:  
Submit the Notice of Death and final **S1107** Treatment Form, **S1107** Adverse Event Form (if the patient was still on protocol treatment) or Follow-Up Form (if the patient was off protocol treatment) documenting death information.

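### PFS is censored at last contact (10.6), so time in contact without a disease assessment counts as progression-free and can bias PFS upward

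*Combined protocol and SAP*

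**What the plan says.** Section 10.6 defines PFS as "From date of registration to date of first documentation of progression or symptomatic deterioration (as defined above), or death due to any cause". For everyone else, "Patients last known to be alive without report of progression are censored at date of last contact". Section 10.5 uses the same last-contact rule for time to death.

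Section 10.2 says that studies with a progression endpoint need whole-body imaging at set intervals to establish that there is no progression. Section 10.2f provides a status of unknown for patients whose target lesions were not assessed.

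The Study Calendar footnotes (Section 9.0) set the schedule: "While on protocol treatment, disease assessments will continue every 8 weeks until progression". They continue: "If patient is removed from protocol treatment prior to disease progression, assessments will be continued on this schedule until disease progression". Scans become discretionary only after progression.

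On data flow, the heading of 14.4d says "IF PATIENT HAS NOT PROGRESSED ONCE OFF PROTOCOL TREATMENT THEN CONTINUE TO SUBMIT EVERY 8 WEEKS UNTIL PROGRESSION". The body under that heading asks for tumor forms and radiology reports only up to documented progression or removal from protocol treatment. Follow-Up Forms run separately under 14.4f: "AFTER OFF TREATMENT, EVERY 3 MONTHS FOR THE FIRST YEAR AND THEN EVERY 6 MONTHS UNTIL DEATH OR FOR A MAXIMUM OF 3 YEARS".

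PFS is a secondary objective (1.2a), estimated by arm, with a stated precision of ±17% at 4 months for 35 patients (11.3). It also enters the conclusion in 11.2: an arm with 8 or more responders is "worthy of further investigation in pRCC if toxicity and PFS data are also supportive". No PFS threshold is given.

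**The concern.** For time to death, a contact proves the status: the patient is alive. For PFS it does not, because target-lesion progression has to be looked for. Under 10.6, a patient who has no further scans but is still known to be alive goes on adding progression-free time. That sits badly with 10.2, which treats unassessed disease as unknown.

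Contact without scans is foreseeable. Section 7.6 allows removal for toxicity, for long holds, at the patient's wish or at the physician's discretion, and 7.8 follows patients for up to three years. A site that follows the body of 14.4d stops sending tumor forms at removal from treatment, while Follow-Up Forms continue. The gap therefore need not come from non-compliance alone.

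Any error has one direction: it makes PFS look better. The ±17% does not cover it. Because PFS must be supportive for a favourable conclusion and no threshold is set, nothing in the plan would reveal the error.

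**Working it through.** **1. The plan's own figures.** The half-width for a proportion near 50% with n = 35 is 1.96 × √(0.5 × 0.5 / 35) = 0.166, which is the stated ±17%. It does not depend on the censoring rule. An exact calculation of the two-stage response design gives alpha 0.0199 and power 0.866, against the stated 2% and 87%. PFS does not enter either.

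**2. When the rule does no harm.** If progression is found at scans, the Kaplan-Meier curve drops only at scan dates. A patient whose last contact comes before the next due scan leaves the risk set before that scan under either rule. The two estimates then agree (difference 0.0 points in simulation). Clinic visits between scans therefore add no bias. Bias needs contact that runs past a missed scan.

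**3. Size when contact outlasts scanning.** From the documents: scans every 8 weeks. Assumed, because the documents give no figures: exponential PFS with median 4 months (17.39 weeks); a fraction f of patients stop scans at a uniform time in weeks 0–24, stay in contact for 26 more weeks, and have no progression reported clinically.

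- True PFS at the week 8, 16 and 24 scans: 2^(−8/17.39) = 0.727; 2^(−16/17.39) = 0.528; 2^(−24/17.39) = 0.384. The last two are the 4- and 6-month values under complete scanning.
- Patients who stop scanning in weeks 0–8, 8–16 or 16–24 have had no scan, the week 8 scan, or the week 8 and 16 scans. Their apparent PFS is (1 + 0.727 + 0.528)/3 = 0.752 at both time points.
- Bias at 4 months = f × (0.752 − 0.528). For f = 10%, 20%, 30% this is 2.2, 4.5, 6.7 points.
- Bias at 6 months = f × (0.752 − 0.384), which gives 3.7, 7.4, 11.0 points.

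Simulation (400,000 patients per scenario, median 4 months) agrees to within 0.1 point and adds other cases. Entries are the last-contact minus the last-assessment estimate, in points, at 4 / 6 months:

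| Stop scans | 13 weeks' contact | 26 weeks' contact | 26 weeks, half of later progressions reported |
|---|---|---|---|
| 10% | 1.9 / 2.4 | 2.2 / 3.7 | 1.5 / 2.5 |
| 20% | 3.9 / 4.9 | 4.5 / 7.4 | 3.1 / 5.0 |
| 30% | 5.9 / 7.6 | 6.7 / 11.1 | 4.8 / 7.8 |

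Over medians of 2, 4 and 7 months, with no clinical reporting, the 4-month gap is 1.3–3.2, 2.6–6.4 and 3.9–9.8 points for 10%, 20% and 30%.

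**4. With deaths as events and contact up to 36 months.** A second simulation (200,000 patients per scenario) assumed median PFS 4 months, scanning stopped at a uniform time in months 0–6, and median survival of 18 months after progression. With 14% of patients (about 5 of 35) unscanned before documented progression:

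- Complete scanning: 52.7%, 38.3%, 14.6% at 4, 6, 12 months.
- Last-contact rule: 56.5%, 44.3%, 23.4%, so the bias is 3.8, 6.0, 8.8 points.
- With 7% unscanned, the bias is about 2, 3, 4 points; with 22%, about 6, 9, 13 points.
- With 14% unscanned, the 4-month bias of 3.8 points falls to 2.3 if 50% of later progressions are captured clinically and to 1.4 if 80% are.

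**5. Whether a one-line change is enough.** Moving only living, progression-free patients to last-assessment censoring gives 55.3%, 42.2%, 19.8%. At 4 months it removes 56.5 − 55.3 = 1.2 of 3.8 points, about a third, because late deaths in unscanned patients still count as events. When those deaths are also censored at the last scan, a parallel run gives 52.9%, 38.4%, 14.8%, against 52.9%, 38.4%, 14.7% with complete scanning. A rule for missed assessments is therefore needed.

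**The case against.** The strongest reply is that the protocol already closes the gap. The Study Calendar continues 8-weekly assessment after treatment stops, until progression, and the heading of 14.4d repeats it. A reader of 14.4f alone might infer that follow-up after treatment is contact without scans. The documents do not support that, since the 3- and 6-monthly forms run alongside the scan schedule. A patient off treatment and unscanned for many months would be a deviation. This stands, and it makes the bias conditional. It does not remove the point, because the body of 14.4d conflicts with that schedule and 10.6 has no rule for missed assessments.

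Second, contact is not blind. Section 14.4g collects progression found off treatment, and symptomatic deterioration, death and physician-judged progression of non-measurable disease are all events. This also stands, and it reduces the size as shown.

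Third, at 4 months, the only PFS time point in the plan, 2–6 points lie well inside ±17. That is true, but the half-width describes random error, and this error always points the same way.

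Fourth, censoring at last assessment is not free of bias. If stopping scans is related to progression, the censoring is informative. With half of later progressions captured clinically, that estimate fell about 0.2–1.5 points below the complete-scanning value at 4 months.

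A reader might also infer that the combination arm is distorted more. The documents do not show this. Section 8.6 keeps patients who cannot tolerate erlotinib on ARQ 197 alone, 11.1 treats each arm as an independent trial, and no comparison of PFS between arms is planned.

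**Conclusion.** The point holds in conditional form. Section 10.6 lets unassessed time count as progression-free, and PFS can be biased upward when contact runs past missed assessments. A reader might infer that PFS is biased as the plan stands. It is not: with 8-weekly scanning kept until progression, the bias is nil.

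Under the assumptions in step 4 of the working, with 7–22% of patients unscanned before documented progression and no clinical capture, it is about 2–6 points at 4 months and 3–9 at 6 months. Clinical reporting makes it smaller. The unscanned share, the median and the capture rate are all assumed; the documents give none of them.

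The response rule, the sample size, alpha and power are unaffected, and unequal bias between arms is not shown. The change is worth making because PFS supports the conclusion in 11.2 without a threshold, and because the correction is cheap.

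**What to change.** In 10.6:

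- Censor patients without documented progression or symptomatic deterioration at the last adequate disease assessment (an objective status other than inadequate), or at registration if there is none.
- Censor there as well when the progression or death follows two or more consecutive missed scheduled assessments. This second sentence is what deals with the late deaths in step 5 of the working.

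Keep last contact for time to death in 10.5. Report PFS under the last-contact rule, with all deaths as events, as a sensitivity analysis. It shows how much the choice matters and addresses informative censoring.

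Reconcile the body of 14.4d with its heading and with the Study Calendar footnote, so that the forms and the assessment schedule end at the same point.

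The cost is a few sentences. Assessment dates are already on the tumor assessment forms. The price is slightly less follow-up, a slightly wider PFS interval and possible informative censoring. If scanning turns out to be complete, the PFS estimate is essentially unchanged.

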## 11.0 STATISTICAL CONSIDERATIONS

### 11.1 Accrual Goal

A parallel (randomized) two-stage design will be used for patient accrual. When conducting both studies in parallel, each study acts independently. Eligible patients with advanced pRCC will be enrolled according to two strata: Strata 1 = 1st line therapy, Strata 2 = 2nd Line therapy. Patients will be randomized to either Arm 1 (single agent ARQ 197) or Arm 2 (ARQ 197+ erlotinib), as long as both arms are open as per stopping rules and toxicity considerations. Each arm will be conducted as an independent clinical trial. The primary endpoint, RECIST response (confirmed CR and PR) will be evaluated every two cycles. There will be no crossover from the single agent arm to the double agent arm.

### 11.2 Analysis of Primary Endpoint

#### Arm 1: ARQ 197 as a single agent (35 patients):

With no activity of ARQ 197 as a single agent in pRCC, we would expect a response rate of 10%. We would consider ARQ 197 promising for further investigation if the response rate were  $\geq 30\%$ . Initially, 20 eligible patients will be accrued to this arm of the study. If 0-1 patients are responders, this would constitute lack of evidence of sufficient activity, and this arm would be closed to accrual. We would expect this to occur 1% of the time if the true probability of response was 30%. If this arm shows adequate activity in the first stage, and toxicity and safety considerations permit, accrual will continue until a total of 35 eligible patients are accrued. If the total number of patients out of 35 who respond is 8+, we would consider this agent promising and worthy of further investigation in pRCC if toxicity and PFS data are also supportive. In this arm, the design has a significance level (probability of falsely declaring that an agent with a 10% response probability is worthy of further investigation) of 2%, and a power (probability of correctly declaring that an agent with a response rate of 30% is worthy of further investigation) of 87%. Thirty five eligible patients are sufficient to estimate the confirmed response to within  $\pm 17\%$  (95% confidence interval).

#### Arm 2: ARQ 197 plus erlotinib (35 patients):

For ARQ 197 as a combination with erlotinib, we have specified the study with the same two-stage design. While the criteria might be considered slightly higher considering the **S0317** data on erlotinib showing responses and prolonged stable disease, raising the bar is considered unwarranted in this case for two main reasons: 1) this study permits pre-treated patients; 2) **S0317**, with only previously untreated patients had 5/52 patients with responses, including unconfirmed responses, and only 29% free from treatment failure at 6 months, suggesting a reasonable probability that erlotinib alone would not pass the first stage in this study. As a result, the same design considerations for Arm 1 apply. The operating characteristics of these rules were described above.

### 11.3 Analysis of Secondary Endpoints

Safety and Tolerability will be summarized by arm by examining the frequency and severity of toxicities grade by the CTCAE v4.0 (Common Terminology Criteria for Adverse Events), the frequency and extent of required dose modifications, and the frequency and cause of patient withdrawal for reasons other than progression.

Thirty five eligible patients are sufficient to estimate the probability of an adverse event within  $\pm 17\%$  (95% confidence interval). Any adverse event occurring with at least a 5% probability is likely to be seen at least once (83% chance).

Assuming an ineligibility rate of approximately 10%, total accrual (eligible + ineligible) to this study is expected to be 78 patients.

Progression-free survival will be estimated by arm. Thirty five eligible patients are sufficient to estimate the 4 month progression-free survival within  $\pm 17\%$  (95% confidence interval).

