### 1.2 Secondary Objectives

- a. To assess the progression free survival (PFS) of patients with locally advanced or metastatic papillary renal cell carcinoma treated with either ARQ 197 or ARQ 197 combined with erlotinib.
- b. To assess the safety and tolerability of ARQ 197 therapy and ARQ 197 combined with erlotinib.
- c. To descriptively assess the role of prior treatment on outcome.

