### 5.2 Prior Therapy Criteria

- \_\_\_\_\_ a. Patients may have received up to one prior systemic therapy for advanced or metastatic renal cell carcinoma. Patients must not have received a MET inhibitor or erlotinib as prior therapy. At least 21 days must have elapsed since completion of prior systemic therapy, 42 days for nitrosoureas or mitomycin C. Patients must have recovered from all associated toxicities at the time of registration.
- \_\_\_\_\_ b. Patients may have received prior radiation therapy, but must have measurable disease outside the radiation port. At least 21 days must have elapsed since completion of prior radiation therapy. Patients must have recovered from all associated toxicities at the time of registration.
- \_\_\_\_\_ c. Patients must not be receiving or planning to receive any other investigational agents.

SWOG Patient No. \_\_\_\_\_

Patient's Initial (L,F,M). \_\_\_\_\_

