## 6.0 STRATIFICATION FACTORS

Patients will be randomized using a dynamic balancing algorithm (15) with stratification based on:  
Prior systemic therapy for advanced or metastatic disease (none vs 1).

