#### 10.5 Time to Death

From date of registration to date of death due to any cause. Patients last known to be alive are censored at date of last contact.

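### Does the lack of a stated analysis for secondary objective 1.2c (role of prior treatment) call for a change to Section 11?

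*Combined protocol and SAP*

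**What the plan says.** Section 1.2 lists PFS (a), safety and tolerability (b), and item c: "To descriptively assess the role of prior treatment on outcome".

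Prior treatment appears in four other places:

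- Section 5.2, eligibility: "Patients may have received up to one prior systemic therapy for advanced or metastatic renal cell carcinoma".
- Section 6.0, the only stratification factor: "Prior systemic therapy for advanced or metastatic disease (none vs 1", so two levels.
- Section 11.1, accrual: "Eligible patients with advanced pRCC will be enrolled according to two strata", first line and second line. The same section says "Each arm will be conducted as an independent clinical trial".
- Section 11.2, Arm 2: the first of two reasons for not setting a higher threshold is that "this study permits pre-treated patients".

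On analysis, Section 11.2 evaluates confirmed response in each arm. Section 11.3 summarises safety by arm and says "Progression-free survival will be estimated by arm". Section 11.4 deals with c-MET and EGFR only. Section 10 defines best response (10.3), PFS (10.6) and time to death (10.5: "From date of registration to date of death due to any cause"). Time to death is not among the objectives in Section 1 and is not mentioned in Sections 11.1 to 11.3.

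**The concern.** A stated objective should lead to a stated analysis. Objectives 1.2a and 1.2b do so and 1.2c does not, although prior therapy is the one factor on which randomisation is balanced. Two choices are left unwritten: which outcome is described, and whether the two groups are shown within each arm or pooled over arms. If those choices were made after the data were seen, the more striking display could be picked. Precision also differs between the two levels, so the choice could affect what the description appears to show. Because Section 11.2 relies on the inclusion of pre-treated patients to justify the Arm 2 threshold, readers will want response by prior therapy.

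**Working it through.** **1. Objective against analysis**

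| Objective | Analysis in Section 11 |
|---|---|
| 1.1 confirmed response | 11.2, per arm, two-stage rule |
| 1.2a PFS | 11.3, by arm |
| 1.2b safety and tolerability | 11.3, by arm |
| 1.2c role of prior treatment | none stated |

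The omission is confirmed.

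**2. What the plan already settles for 1.2c**

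- *Mode:* descriptive, so no test, model or error rate is implied.
- *Grouping:* none or one prior systemic therapy (6.0). Section 5.2 allows no third level. The group is known for every randomised patient.
- *Outcome:* not named, but confirmed response (1.1) and PFS (1.2a) are the only efficacy endpoints among the objectives.
- *Level:* not stated for 1.2c, but 11.1 treats the arms as independent trials and 11.3 summarises by arm. Within arm is the default.

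**3. The plan's own figures reproduce**

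- Half-width at n = 35 and p = 0.5: 1.96 × √(0.25/35) = 0.166, stated as ±17%.
- Two-stage rule (20 patients, stop at 0–1 responders; 35 in total, success at 8 or more): P(success) = Σ over x = 2 to 20 of P(X₂₀ = x) × P(X₁₅ ≥ 8 − x). This gives 0.0199 at a true rate of 10% (stated 2%) and 0.866 at 30% (stated 87%).

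Neither calculation uses prior therapy, so nothing decided about 1.2c can move them.

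**4. How much the level of summary matters**

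The documents give no share of pre-treated patients. Assume 20% to 50%, with 35 eligible per arm and p = 0.5. Half-width = 1.96 × √(0.25/n).

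| Pre-treated share | n within arm | Half-width | n pooled | Half-width |
|---|---|---|---|---|
| 20% | 7 | 37 points | 14 | 26 points |
| 30% | 10.5 | 30 points | 21 | 21 points |
| 40% | 14 | 26 points | 28 | 19 points |
| 50% | 17.5 | 23 points | 35 | 17 points |

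An arm that closes after 20 patients (probability 0.392 at a true 10%) would have 6 patients in the smaller group at 70:30 and 10 at 50:50, with half-widths of about 40 and 31 points. Pooling narrows the interval, but it mixes ARQ 197 alone with ARQ 197 plus erlotinib.

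**5. Would the choice change a reading against 10% and 30%?**

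One can find counts for which it would. Exact 95% intervals are 1.5% to 36.4% for 2/17 within an arm, which covers both rates, and 3.2% to 26.7% for 4/35 pooled, which excludes 30%. Neighbouring counts undo the contrast:

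- 1/17 within an arm: 0.1% to 28.7%, which excludes 30% without pooling.
- 5/35 pooled: 4.8% to 30.3%, which does not exclude 30%.
- At 70:30, 2/21 pooled: 1.2% to 30.4%, which does not exclude 30%.
- For zero responders the upper limit is 1 − 0.025^(1/n): 30.8% for 0/10 and 28.5% for 0/11, so one more patient reverses the reading.

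The pattern belongs to the counts chosen. The comparison is also not one the plan makes: 10% and 30% are design rates for a whole arm, and they are not set for a prior-therapy group or for patients pooled over two regimens.

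**The case for a change.** The strongest case for a change is that calling an analysis descriptive rules out a test but fixes neither the outcome nor the level of summary. The plan names method families even for the exploratory biomarker work, which Section 1.3 makes conditional on funding, yet says nothing for a stated secondary objective. Section 11.2 makes pre-treatment relevant to interpreting Arm 2. One sentence would close the gap, with no new data.

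Much of this stands. The sentence is missing, the level does affect precision at every mix examined, and adding it would cost almost nothing.

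What does not stand is a consequence large enough to require it. The within-arm default can be read from Sections 11.1 and 11.3, and the outcomes from Section 1. The remark on pre-treated patients in Section 11.2 explains a threshold fixed in advance for the whole arm, and that threshold does not depend on response by prior therapy. The silence on time to death agrees with the objectives, which do not include survival, so it is weak evidence of a gap. A required pooled table would add a display that the independent-arm design does not call for.

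**Conclusion.** This is a gap in documentation that an analyst fills sensibly: confirmed response and PFS described by prior therapy (none or one) within each arm, with intervals and no test. A pooled display is optional; if shown, it belongs beside the within-arm figures because it combines two regimens.

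The size of what is left open is the difference between half-widths of about 23 and 17 points if the groups are equal, or about 37 and 26 points for a group making up 20% of patients. These figures assume 35 eligible patients per arm and a mix that the documents do not give. Neither level supports a firm statement about prior treatment, and the plan asks for none. No stated figure, decision rule or conclusion changes, so no amendment is needed.

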
unfavorable clinical characteristics. (7) This study included a significant number of patients with non-clear cell histology. In a subset analysis that included 55 patients with pRCC, median PFS was 7 months. These outcomes in patients with non-clear RCC compare with the RR of 39% and median PFS of 11 months reported in a pivotal Phase III trial of patients with cRCC treated with sunitinib. (8) Dual c-MET/VEGFR-2 inhibitor foretinib demonstrated 13.5% response rate and median PFS of 9.3 months. Responses were significantly more common in patients with germline mutations. (9) Overall the analysis of available data suggests that clinical benefit of targeted agents, although present in pRCC, is inferior to the one observed in clear cell histology.

Preclinical data indicates that absence of VHL mutations (VHL mutations are typically not seen in pRCC) is associated with greater activity of epidermal growth factor receptor (EGFR) inhibitors in RCC. (10) Based on that observation, the oral EGFR inhibitor erlotinib has been evaluated in a Phase II trial of patients with metastatic pRCC in SWOG. (11) Patients with histologically confirmed advanced or metastatic pRCC received erlotinib at 150 mg po q day until disease progression. Thirty nine patients were evaluable for response. With a median follow-up of 12.8 months; four patients had confirmed PR for RR of 10%. Median overall survival was 26.9 months. Probability of freedom from treatment failure at 6 months was 29%. There was one Grade 5 adverse event (AE) of pneumonitis and one Grade 4 thrombotic event. As expected only two patients (2/35) demonstrated mutations in vHL gene confirming that pRCC is typically associated with wild-type vHL. All but one specimen stained positive for EGFR (17/18) but no association was observed between EGFR score or staining intensity with clinical outcome. This suggests that mutational status, receptor amplification or differential intracellular signaling mechanisms may play a more significant role in predicting clinical benefit from EGFR-directed therapies. These findings were consistent with those of EGFR therapy in other diseases. Overall results of this study demonstrated activity of erlotinib in patients with pRCC and in the absence of an obvious superior alternative support further evaluation of erlotinib either alone or in combination with therapies targeting other relevant pathways in patients with pRCC.

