### 13.0 REGISTRATION GUIDELINES

#### 13.1 Registration Timing

Patients must be registered prior to initiation of treatment (no more than five working days prior to planned start of treatment).

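### Is 4 months a badly placed time point for progression-free survival because it falls only days after the second scan?

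*Combined protocol and SAP*

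**What the plan says.** Section 11.3 plans an estimate of PFS for each arm. One sentence on precision follows: 35 eligible patients are "sufficient to estimate the 4 month progression-free survival within" ±17% with 95% confidence. That sentence holds the only PFS time point in the statistical section.

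Section 10.6 starts the clock at registration: "From date of registration to date of first documentation of progression or symptomatic deterioration", or death from any cause, with patients alive and progression-free censored at last contact. Section 13.1 allows registration "no more than five working days prior to planned start of treatment". On scans, the footnotes to the Section 9.0 calendar say "Tumor assessment will be done after every second cycle by the same method used at baseline". A cycle is 28 days (Section 7.1), and the calendar places assessments in weeks 9, 17 and 25. They continue every 8 weeks until progression, also in patients who have stopped treatment. No tolerance around the scan dates is given.

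The one landmark rate in the documents comes from the earlier erlotinib trial: "Probability of freedom from treatment failure at 6 months was 29"% (Section 2.0), repeated in Section 11.2, Arm 2, as "only 29% free from treatment failure at 6 months".

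Under Section 11.2, Arm 1, an arm with at least 8 responders out of 35 is called promising provided that toxicity and PFS support it. No PFS value or time point is attached to that condition.

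**The concern.** A landmark just after a scheduled scan is fragile. Progression is usually dated to the scan that shows it. A patient who progresses between scans 1 and 2 counts as event-free at 4 months if scan 2 slips past day 121.75, and the margin is only 3 to 10 days. Late scans can push the 4-month figure only upward, so the error is a bias that the ±17% interval does not cover.

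The figure would also stand alone, because no 4-month rate is given for comparison. PFS plays some part in calling an arm promising, so an inflated figure might make an arm look better than it is. Six months lies further from its scan and has a published figure at the same time point, so it looks like the natural choice.

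**Working it through.** **The plan's own figure.** The largest half-width with n = 35 is at p = 0.5: 1.96 × √(0.25/35) = 0.166, which is the stated ±17%. It is the same maximum at any landmark; at p = 0.29 it is 1.96 × √(0.29 × 0.71/35) = 0.150.

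**Scan dates against landmarks.** A month is 365.25/12 = 30.44 days, so 4 months is day 121.75 and 6 months is day 182.6. Scans fall 56, 112 and 168 days after treatment starts. Five working days are up to 7 calendar days, so from registration:

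- scan 2 is due on day 112 to 119, which is 2.8 to 9.8 days before the 4-month point;
- scan 3 is due on day 168 to 175, which is 7.6 to 14.6 days before the 6-month point.

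The margin at 6 months is wider by about 5 days. These dates take the scan on the first day of the calendar week. If it may fall on any day of week 17, it can come up to 3.2 days after the 4-month point.

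**With on-time scans.** Assume exponential PFS with a 4-month median and a lag from registration to treatment spread evenly over 0 to 7 days (average 3.5 days). If every event is found at a scan:

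- 4 months: apparent 0.5^(115.5/121.75) = 51.8%, true 50.0%, error +1.8 points;
- 6 months: apparent 0.5^(171.5/121.75) = 37.7%, true 0.5^1.5 = 35.4%, error +2.3 points.

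The wider margin at 6 months costs a little accuracy when scans are on time.

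**With scans off schedule.** The documents give no scan-delay data, so the delays are assumptions. The medians run from 3.4 months, implied by 29% at 6 months (6 × ln 2 / −ln 0.29 = 3.36), to 7 months, the papillary subset in Section 2.0. The shifts come from simulating 400,000 patients per scenario with all events found at scans. They are in percentage points against on-time scans:

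| Scan timing | 4-month PFS | 6-month PFS |
|---|---|---|
| within ±3 days | 0 | 0 |
| within ±7 days | +1 to +2 | 0 |
| 0–7 days late | +2 to +3 | about −1 |
| every scan 7 days late | +6 to +10 | about −1 |
| 0–14 days late | +6 to +10 | +1 to +2 |
| 0–7 days added at each scan | +7 to +10 | +3 to +4 |
| every scan 14 days late | +10 to +15 | +7 to +9 |

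A hand check of the ±7-day row: scan 2 passes day 121.75 only when lag plus deviation exceeds 9.75 days. The probability is (4.25²/2)/(7 × 14) = 9.2%. With a 4-month median, 19.8% of patients progress between days 56 and 112, so the shift is about 0.092 × 19.8 = 1.8 points. That agrees with the table.

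The table overstates the effect to the extent that events are found without a scan. Section 10.6 also counts symptomatic deterioration and death, and Section 8.3 has patients seen every two weeks for eight weeks and then every four. If 30% of events are dated when they occur, the 4-month shift with scans 0–14 days late falls to +4 to +7.

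**What depends on the 4-month figure.** Nothing in Section 11 does. The primary endpoint is confirmed response, and its stopping and success rules use response counts. The PFS condition in Section 11.2 names no time point. Section 10.6 defines a censored time-to-event endpoint and scans continue until progression, so the median and the 6-month rate come from the same data.

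**The case for a change.** The strongest case for a change is that delays tend to run one way, that treatment may be held for up to 21 days, and that the calendar footnotes tie scans both to cycles and to 8-week intervals. If holds stretched the cycles and scans followed them, delays could build up. Four months would then move by 7 to 10 points and 6 months by only 3 to 4. Naming 6 months in advance would cost a few sentences and limit the choice of time point after the data are seen.

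It is true that 6 months is less sensitive to late scans in every late-scan scenario examined, and that no scan window is stated. The rest is weaker. Section 7.1 allows no pause between cycles, and the footnotes fix the 8-week interval. Six months still moves by 7 to 9 points if every scan is 14 days late, so changing the landmark does not remove the cause.

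Six months gains no sound comparator either. The 29% is freedom from treatment failure, which these documents do not define, and it comes from a trial "with only previously untreated patients had 5/52 patients with responses". Here, "Patients may have received up to one prior systemic therapy for advanced or metastatic renal cell carcinoma". Section 11.2 itself uses that difference in population to justify not raising the response criterion for Arm 2. The closest PFS figures in Section 2.0 are medians, which can be set beside the estimated curve whichever landmark is stressed.

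A sensitivity analysis that dates progression to the scheduled scan, or uses interval censoring, is a reasonable optional extra. It departs from the date-of-documentation definition in Section 10.6, and leaving it out makes no planned result wrong.

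**Conclusion.** The concern does not hold. The 4-month point does fall 3 to 10 days after the second scan is due, but the plan uses it only to illustrate precision, and the ±17% is right. No test, threshold or go/no-go rule rests on it, and 6-month PFS is available from the planned estimate without an amendment.

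With scans within a week either side of schedule, the 4-month figure moves by at most about 2 points, against a half-width of about 17. Shifts of 6 points or more need systematic one-sided delay, which is an assumption and not something the documents report. These sizes rest on exponential PFS with medians of 3.4 to 7 months, a lag of 0 to 7 days from registration to treatment, and all events found at scans, which enlarges them. Statisticians may reasonably differ on which landmark to stress for an untested secondary endpoint.
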